14.1.1.1.2. Secondary Efficacy Endpoint

The secondary efficacy endpoint is:

Survival at 14 months of age amongst symptomatic SMA Type 1 patients who are homozygous negative for *SMN1* exon 7 and have 2 copies of *SMN2* without the *SMN2* genetic modifier.

Survival is defined by the avoidance of the combined endpoint of either (a) death or (b) permanent ventilation, which is defined by tracheostomy or by the requirement of ≥ 16 hours of respiratory assistance per day (via non-invasive ventilator support) for ≥ 14 consecutive days in the absence of an acute reversible illness, excluding perioperative ventilation. Permanent ventilation, so defined, is considered a surrogate for death.

- An “acute reversible illness” is defined as any condition other than SMA that results in increased medical intervention (i.e., increased requirement for respiratory support; use of other concomitant medications as rescue) requirements and is expected to be reversible or improved following definitive intervention (i.e., surgery, antibiotics) or introduction of escalated supportive care, such as hospitalization (i.e., for upper respiratory infection, spontaneous fracture). The specific duration of the condition antecedent intervention

shall not be considered in the definition of “acute.” The date of “definitive intervention” shall be defined as the date of provision of a procedure (i.e., surgery, etc.) or medication (i.e., antibiotics) intended to cure or substantially improve the condition. For conditions such as viral respiratory infections for which supportive care is provided, the date of “definitive intervention” shall be considered the date of hospitalization or substantial escalation of care.

- “Perioperative” use reflects any alteration of ventilator use related to a surgical or other medical procedure of any nature for which the patient received medications that could impair or interfere with respiratory function.
- For a patient who develops an acute reversible illness and/or requires perioperative ventilator support, a recovery period not to exceed 21 days following the date of definitive intervention will be instituted. Following this recovery period, the condition will be considered subacute and the patient will become evaluable with regards to the surrogate survival endpoint (requirement of ventilator support of ≥ 16 hours/day for 14 or more days).

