5.6. PNCR Control Population

The PNCR Natural History dataset is drawn from a large natural history study ([Finkel, 2014](#)) performed on a large cohort of 337 patients with any form of spinal muscular atrophy followed at 3 large, internationally recognized tertiary medical centers with significant expertise in the management of SMA (Harvard University/Boston Children's Hospital, Columbia University and the University of Pennsylvania/Children's Hospital of Philadelphia). Previously identified patients followed in PNCR site clinics and newly diagnosed patients were enrolled. All eligible patients were offered participation in the PNCR study. Study visits were scheduled at baseline and at 2, 4, 6, 9, and 12 months and every 6 months thereafter. The SMA standard of care

guidelines ([Wang, 2007](#)) were used as a basis for providing uniform care among the study sites. For purposes of this study, sitting (for SMA Type 2) was defined as being able to sit independently for >10 seconds; children who were unable at any point to achieve this milestone were classified as SMA Type 1.

A natural history control population is drawn from the PNCr Natural History Dataset ([Finkel, 2014](#)) consisting of all patients with age of onset ≤ 6 months, bi-allelic deletion of *SMN1* (exon 7/8 common homozygous deletion) and 2 copies of *SMN2* for whom enrollment data (retrospective and prospective) is available to determine survival based on the defined criteria. The *SMN2* modifier mutation (c.859G>C) described by Prior and colleagues (Prior, Thomas W., et. al. "A positive modifier of spinal muscular atrophy in the *SMN2* gene." *The American Journal of Human Genetics* 85.3 (2009): 408-413.) was not assessed in the PNCr study cohort. Based on these criteria, 23 patients from the PNCr dataset are included in the control population. Among them, 16 patients reached the combined endpoint of death or the need for a minimum of 16 hours/day of noninvasive ventilation support for a minimum of 14 continuous days by 14 month of age and one patient discontinued the study at age of month 4. The survival rate at 14 months of age is approximately 25% (6/23), of which the control cohort will be used as comparator with ITT population for survival analysis.

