6.2.4.2. Supportive (Secondary and exploratory) Efficacy Variables

The secondary efficacy endpoint, event-free survival, is defined as avoidance of any one of the following events up to 14 months of age, whichever occurred first:

- Death, *or*
- Tracheostomy, *or*
- Noninvasive Ventilatory support ≥ 16 -hour per day *and* continuously ≥ 14 days

Usage data for patients using non-invasive ventilatory support will be extracted directly from the device (e.g., Trilogy 100, Trilogy 200, ResMed Stellar) on an SD card, or USB stick and transferred as an external dataset, if available. Average daily use of non-invasive ventilatory support at baseline and monthly be summarized from data recorded on an SD card or USB stick and submitted in a format that is evaluable. If a patient did not have a device with the capability to record usage data at baseline and was using non-invasive ventilatory support prior to screening, the daily usage will be documented in the source documentation. As a secondary analysis, the amount of ventilation support will be categorized into None, $>0-\leq 12$ hours, $>12-\leq 16$ hours, ≥ 16 or permanent ventilation. At each of the above time points, the count and percent of patients in each ventilation support category will be presented.

Supportive (exploratory) efficacy variables are as follows:

- CHOP-INTEND summary score: This is assessed by evaluating the Baseline CHOP-INTEND scores compared to each scheduled visit time points (see [Table 4](#)), collected from patient's CRF. A summary score is obtained by summing the individual best-side scores.
- Achievement of Selected Threshold Scores on CHOP-INTEND: clinically relevant threshold scores were determined for categorizing CHOP-INTEND summary scores: ≥ 40 , ≥ 50 , ≥ 58 .
- Bayley Scales of Infant and Toddler Development[®] version 3: Two domains of motor and adaptive behavior will be assessed from patient's CRF at scheduled visits (see [Table 1](#)) with both raw and scaled scores provided.
- Age at which independent sitting (for 10 seconds) is first achieved.
- Ability to remain independent of ventilator support, defined as requiring no daily ventilator support/usage at 18 months of age.
- Ability to thrive as defined by maintaining the ability to swallow and to maintain weight ($>$ third percentile based on WHO CGRS without need of gastrostomy or other mechanical or non-oral nutritional support at 18 months of age)

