8.2. Secondary Efficacy Endpoints and Analysis

8.2.1. Secondary Efficacy Endpoint: Avoidance of Death or Surrogate for Death (Permanent Ventilation)

The secondary efficacy endpoint is defined by avoidance of the combined endpoint of either (a) death or (b) permanent ventilation, defined as requirement of tracheostomy or ≥ 16 hours of respiratory assistance per day (includes non-invasive ventilatory support) continuously for ≥ 14 days in the absence of an acute reversible illness, excluding perioperative ventilation. Permanent ventilation, so defined, is considered a surrogate for death.

Non-invasive ventilatory support usage data (only available from Trilogy 100) will be extracted directly from each patient's device; the data will be downloaded from the device's SD card through software provided by the manufacturer and transferred as an external dataset.

An "acute reversible illness" is defined as any condition other than spinal muscular atrophy that results in increased medical intervention (i.e., increased requirement for external ventilator support; use of other concomitant meds as rescue) requirements and is expected to be reversible or improved following definitive intervention (i.e., surgery, antibiotics) or introduction of escalated supportive care, such as hospitalization (i.e., for upper respiratory infection, spontaneous fracture). The specific duration of the condition antecedent intervention shall not be considered in the definition of "acute". The date of "definitive intervention" shall be defined as the date of provision of a procedure (i.e., surgery, etc.) or medication (i.e., antibiotics) intended to cure or substantially improve the condition. For conditions, such as viral respiratory infections, for which supportive care is provided, the date of "definitive intervention" shall be considered the date of hospitalization or substantial escalation of care.

"Perioperative" use reflects any alteration of ventilator use related to a surgical or other medical procedure of any nature for which the participant received medications that could impair or interfere with respiratory function.

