For a participant who develops an acute reversible illness and/or requires perioperative ventilator support, a recovery period not to exceed 21 days following the date of definitive intervention will be instituted. Following this recovery period, the condition will be considered sub-acute and the participant will become evaluable with regards to the surrogate survival endpoint (Requirement of ventilator support of ≥ 16 hours/day for greater than 14 days).

Example: Using this approach it would mean that on day 1, patient A receives definitive intervention for an acute reversible illness resulting in ventilator support for ≥ 16 hours/day. Days 1-21 will be provided to permit recovery from the acute reversible illness. On Day 22, the participant is no longer considered to have an acute illness. Should the participant continue to require ≥ 16 hours/day of ventilator support from day 22 to day 36, he or she shall be considered to meet the surrogate endpoint.

Statistical approach: The proportion surviving event-free to 14 months of age will be computed in the ITT population. Patients who terminate the study prior to reaching 14 months of age for any reason will be considered treatment failures (event).

As a comparator, in a natural history study of SMA Type 1 patients, [Finkel et al \(2014\)](#), 16 patients reached the combined endpoint of death or the need for a minimum of 16 hours/day of noninvasive ventilation support for a minimum of 14 continuous days by 14 month of age, one patient discontinued the study at age of month 4 and 6 patients event-free survived at age of 14 months.

The observed proportion surviving in the current study will be compared to the natural history data (5) of the matching cohort, using a 2-sided Fisher's Exact test, along with the corresponding 95% confidence intervals.

The number of patients survived in each subgroups specified in [Section 6.7](#) will be provided.

Time to death or permanent ventilation through 14 months of age is an additional sensitivity analysis. In case there is at least 1 patient who is event-free, but discontinue study prior to 14-months of age, a sensitivity analysis, based on the approach for time to event, will be carried out. In this analysis, time to event will be censored at 14 months of age or at the date of

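### The SAP states the PNCR ventilation event without the acute-illness and perioperative exemption given to treated infants, does not say which rule produced the 16 control events, and plans no analysis on one common rule

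*SAP*

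**What the plan says.** **Treated infants.** Protocol 14.1.1.1.2 counts tracheostomy as an event. It also counts non-invasive support of at least 16 hours a day for at least 14 "consecutive days in the absence of an acute reversible illness, excluding perioperative ventilation". SAP 8.2.1 carries the same exclusion: "in the absence of an acute reversible illness, excluding perioperative ventilation". Both documents add that after such an illness or procedure "a recovery period not to exceed 21 days following the date of definitive intervention will be instituted". Only then can ventilation count again. The SAP's worked example reaches the event when support continues from day 22 to day 36.

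**PNCR controls.** SAP 5.6 describes the control events as death or a "need for a minimum of 16 hours/day of noninvasive ventilation support for a minimum of 14 continuous days by 14 month of age". SAP 8.2.1 repeats this just before the Fisher comparison: "16 patients reached the combined endpoint of death or the need for a minimum of 16 hours/day of noninvasive ventilation support". Neither sentence mentions an exemption, a recovery period or tracheostomy. SAP 5.6 gives 23 controls: 16 events, one discontinuation at month 4 and 6 survivors. The 16 are not split into deaths and ventilation.

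**Two places that bear on how to read this.** SAP 5.6 selects controls for whom enrollment data "is available to determine survival based on the defined criteria", without saying which criteria are meant. SAP 6.2.4.2 lists the treated-infant event as death, tracheostomy or "Noninvasive Ventilatory support ≥ 16 -hour per day" for 14 days, also without the exemption.

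**The concern.** A comparison with an external control is only as sound as the match between the two event definitions. Taken as written, an infant with at least 14 days of support at 16 hours a day or more, all within an acute illness and its recovery period, is an event in PNCR and a survivor if treated. Protocol 5.5 expects respiratory infections in the enrolled infants, and both documents use respiratory infection as an example of an exempt illness, so the exemption can come into play. Neither document says how often it would.

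Applying the exemption requires a dated intervention and daily ventilation hours. Treated infants have roughly monthly visits and, for some, device downloads. After baseline, PNCR visits were at 2, 4, 6, 9 and 12 months and then every six months, with partly retrospective data. The SAP does not show that controls could be, or were, judged in the same way.

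The planned survival sensitivity analysis in SAP 8.2.1 changes the censoring and uses Kaplan-Meier and log-rank methods. It leaves both event definitions as they are.

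**Working it through.** **Inputs.** 25 treated infants, 80% treated survival and 25% control survival (SAP 3.7); 23 controls with 6 survivors (SAP 5.6); two-sided Fisher's exact test at 0.05 (SAP 3.11.2).

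**1. The plan's own figures.** Control survival is 6/23 = 26.1%, which the SAP rounds to about 25%. Exact power is the sum, over all pairs of treated and control survivor counts with Fisher p ≤ 0.05, of the product of the two binomial probabilities. At 80% against 25% it is 97.6% for 25 against 23, and 97.9% for 25 against 25. The stated power (more than 90% in SAP 3.7 and protocol 14.2, at least 95% in the protocol synopsis) is reproduced.

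**2. Which courses are scored differently.** Under the PNCR wording the event is reached after 14 days. For a treated infant with an exempt illness, the recovery period is at most 21 days from definitive intervention, so the latest event point is 21 + 14 = 35 days after it under the protocol's 14 or more days. (The SAP text says greater than 14 days, and its example of day 22 to day 36 is 15 days.) The 21 days are a cap. A course that outlasts the recovery period by the required days is an event in both groups; only shorter courses diverge.

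**3. Effect on the test.** The number of PNCR events that would be exempt under the treated-arm rule is not given. Let k be that number, as an assumption. Control survival is then (6 + k)/23, and each event moves it by 1/23 = 4.3 points. Power takes 80% treated survival and the control rate in the row.

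| k | Control survival | Survivors needed of 25 | Fisher p at 20/25 | Difference at 20/25 (points) | Power |
|---|---|---|---|---|---|
| 0 | 6/23 = 26.1% | 14 (p=0.045) | 0.0004 | 53.9 | 96.9% |
| 1 | 7/23 = 30.4% | 15 (p=0.049) | 0.0011 | 49.6 | 93.4% |
| 2 | 8/23 = 34.8% | 17 (p=0.042) | 0.0030 | 45.2 | 87.8% |
| 3 | 9/23 = 39.1% | 18 | 0.0072 | 40.9 | 79.9% |
| 4 | 10/23 = 43.5% | 19 | 0.016 | 36.5 | 69.8% |
| 5 | 11/23 = 47.8% | 20 | 0.034 | 32.2 | 58.4% |
| 6 | 12/23 = 52.2% | 21 | 0.066 | 27.8 | 46.4% |

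Deaths cannot be reclassified, and a control who had an exempt episode but died before 14 months remains an event. So k is limited to controls who counted through ventilation alone.

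**4. The same question from the treated side.** Removing the exemption can turn treated survivors into events, each costing 1/25 = 4.0 points. Starting from 20/25 against 6/23, significance holds down to 14/25 (p=0.045) and is lost at 13/25 (p=0.083).

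**The case against.** The strongest objection is that silence is not evidence of a different rule. The reference in SAP 5.6 to defined criteria may mean the trial definition, and SAP 6.2.4.2 drops the exemption for treated infants too, so a short form may simply be how this SAP writes the event. That stands. A reader might infer that the PNCR events were in fact counted with no exemption; the documents do not establish this. They do show that the exemption is set out in full for treated infants and never for controls.

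A reader might also infer a bias towards AVXS-101. A one-sided exemption would work that way, but the PNCR wording omits tracheostomy as well. If that omission is literal, a control with a tracheostomy could count as a survivor, which works against AVXS-101. The net direction cannot be settled from the text.

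It is also fair to say that the planned result is robust, that the endpoint is secondary and tested only after the primary succeeds, and that the SAP already reports death and permanent ventilation separately, tabulates ventilation categories (6.2.4.2) and allows further natural-history comparisons (4.7). None of these puts both groups on one rule, and the comparison in 4.7 is optional and unspecified.

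**Conclusion.** The point holds as a gap in what the SAP specifies. The written event rules differ between the groups, the rule behind the 16 PNCR events is not stated, and no planned analysis uses a common rule.

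The size is conditional on an unknown. If one or two control events would be exempt, the bar rises from 14 to 15 or 17 survivors of 25, the difference at 20/25 falls from 53.9 to 49.6 or 45.2 points, and at two events power drops below 90%. Significance at 20/25 is lost only at six. At the planned effect the conclusion of the test is therefore unlikely to turn on this; the main risk is a biased estimate of the survival difference, in an uncertain net direction. The counts of reclassified events are assumptions, and the 35-day figure is an upper limit.

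**What to change.** **Sensitivity analysis.** Add to SAP 8.2.1 an analysis that counts as an event in treated infants death, tracheostomy, or at least 16 hours a day of support for at least 14 continuous days with no exemption. Keep tracheostomy in the list; copying the PNCR wording literally would loosen the treated endpoint. Use device data where available and eCRF-recorded usage (protocol 12.1.7) otherwise, because SAP 8.2.1 says that device data come only from one ventilator model. Report the Fisher test and the difference beside the main result.

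**Control events.** State in SAP 5.6 which rule produced the 16 PNCR events, including how tracheostomy was handled, and give their split into death and ventilation. Where PNCR records allow, reclassify them under protocol 14.1.1.1.2.

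**Cost.** A few programming days on data the trial already collects, plus a check of the PNCR records. The survival difference may come out slightly less favourable.

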8.2. Patient Exclusion Criteria

Patients must not meet any of the following exclusion criteria:

1. Previous, planned or expected scoliosis repair surgery/procedure prior to 18 months of age
2. Use of invasive ventilatory support (tracheotomy with positive pressure) or pulse oximetry < 95% saturation at screening
 - a. Pulse oximetry saturation must not decrease ≥ 4 percentage points between screening and dosing with confirmatory oximetry reading
 - b. Patients may be put on non-invasive ventilatory support for < 12 hours per day at the discretion of their physician or trial staff
3. Use or requirement of non-invasive ventilatory support for ≥ 12 hours daily in the 2 weeks prior to dosing
4. Patient with signs of aspiration based on a swallowing test or whose weight-for-age falls below the 3rd percentile based on WHO Child Growth Standards [42] and unwilling to use an alternative method to oral feeding
5. Active viral infection (includes human immunodeficiency virus [HIV] or positive serology for hepatitis B or C, or known Zika virus infection)
6. Serious non-respiratory tract illness requiring systemic treatment and/or hospitalization within 2 weeks prior to screening

7. Upper or lower respiratory infection requiring medical attention, medical intervention, or increase in supportive care of any manner within 4 weeks prior to screening
8. Severe non-pulmonary/respiratory tract infection (e.g., pyelonephritis, or meningitis) within 4 weeks before administration of gene replacement therapy or concomitant illness that, in the opinion of the Principal Investigator, creates unnecessary risks for gene replacement such as:
 - a. Major renal or hepatic impairment
 - b. Known seizure disorder
 - c. Diabetes mellitus
 - d. Idiopathic hypocalcuria
 - e. Symptomatic cardiomyopathy
9. Known allergy or hypersensitivity to prednisolone or other glucocorticosteroids or their excipients.
10. Concomitant use of any of the following: drugs for treatment of myopathy or neuropathy, agents used to treat diabetes mellitus, or ongoing immunosuppressive therapy, plasmapheresis, immunomodulators such as adalimumab, or immunosuppressive therapy within 3 months prior to gene replacement therapy (e.g., corticosteroids, cyclosporine, tacrolimus, methotrexate, cyclophosphamide, IV immunoglobulin, rituximab)

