5.2. Intent-to-Treat (ITT) Population

The ITT population will consist of symptomatic patients with bi-allelic deletion of *SMN1* (exon 7/8 common homozygous deletions) and 2 copies of *SMN2* without the known gene modifier mutation (c.859G>C) who receive an IV infusion of AVXS-101 at less than 180 days of age.

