6.2. Key Definitions

6.2.1. Definition of Baseline

The baseline value refers to the last non-missing measurement collected before gene therapy infusion of study drug. On Study Day 1, all assessments should be performed prior to administering the gene therapy infusion of study drug per protocol. The baseline value is therefore determined by the last non-missing measurement collected on or before the first day of study drug administration. If multiple measurements are recorded on the same day, the last measurement recorded prior to the gene therapy infusion will be used as the baseline value. If these multiple measurements occur at the same time or time is not available, then the average of these measurements (for continuous data) or the worst among these measurements (for categorical data) will be considered as the baseline value. This same baseline value will be used for the treatment and post-treatment periods.

The baseline values will be the first non-missing values collected for the control patients from the PNCR dataset.

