discontinuation. The survival rate at 14 months of age will be estimated by Kaplan-Meier method, and survival curves for AVXS treated patients and the PNCr cohort will be compared using log-rank test at significance level of 0.05.

Additionally, the proportion of patients who experience each of the following events by 14 months of age will be summarized:

- Death
- Permanent ventilation

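### Survival comparison: the plan does not show that treated infants and the 23 natural-history controls start to be counted at comparable ages, and its log-rank check states no delayed entry

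*SAP*

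**What the plan says.** **Treated infants.** SAP 5.2 limits the ITT population to symptomatic infants of the specified genotype "who receive an IV infusion of AVXS-101 at less than 180 days of age". Protocol 8.2 also excludes invasive ventilation at screening and non-invasive support for 12 or more "hours daily in the 2 weeks prior to dosing".

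**Controls.** SAP 5.6 takes every PNCR patient with onset by 6 months of age and the genotype "for whom enrollment data (retrospective and prospective) is available to determine survival based on the defined criteria". On recruitment it says: "Previously identified patients followed in PNCR site clinics and newly diagnosed patients were enrolled". This gives 23 controls: 16 with an event by 14 months, one who left at 4 months of age, and 6 event-free. The comparator follows: "The survival rate at 14 months of age is approximately 25% (6/23), of which the control cohort will be used as comparator". No enrolment age and no event-free-at-entry condition is given. SAP 6.2.1 adds only this: "The baseline values will be the first non-missing values collected for the control patients from the PNCR dataset".

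**Matching.** The protocol synopsis, in the sentence that defines the secondary comparison, describes the controls as matched on age and gender. Protocol 14.2 repeats this. Protocol 14.3.2 and SAP 3.7 do not mention it. SAP 8.2.1 speaks of a matching cohort without a rule.

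**Analysis.** The formal test is a two-sided Fisher's exact test. SAP 8.2.1 then says: "Time to death or permanent ventilation through 14 months of age is an additional sensitivity analysis". Its next sentence ties the analysis to at least one event-free patient discontinuing before 14 months. Times are censored at 14 months of age or at discontinuation, and "survival curves for AVXS treated patients and the PNCr cohort will be compared using log-rank test".

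**The concern.** A treated infant cannot have a counted event before infusion. Whether a control can have one before a comparable age depends on when PNCR observation starts, and the plan does not say. If controls are in effect counted from birth, their early events have no possible counterpart in the treated group, which favours AVXS-101. If controls had to survive to a PNCR enrolment later than the infusion ages, the comparison works against it.

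A log-rank test on the age scale without delayed entry is more exposed than the Fisher test. It sets each early control event against a treated risk set that includes infants not yet infused, who could not have failed. The analysis meant to support the Fisher result could therefore be the less reliable of the two. Survival is the only other hypothesis in the testing hierarchy (SAP 8.4), and its curves and estimate will be read along with the p-value.

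**Working it through.** **1. The plan's own figures.** SAP 3.7 and protocol 14.2 state power above 90%, and the synopsis at least 95%, for 80% against 25% with 25 treated, two-sided Fisher, alpha 0.05. Exact enumeration gives 97.9% for 25 against 25 and 97.6% for 25 against 23, so both statements hold. The counts add up (16 + 1 + 6 = 23), and 6/23 = 26.1%.

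**2. What entry age alone can do.** Neither document gives control entry or event ages, so what follows is a range under assumptions, with the same hazard in both groups.

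- Hazard: constant, with 75% failing by 13.6 months (SAP 3.7). λ = ln(4)/13.6 = 0.1019 per month and S(14) = exp(−14λ) = 0.2400.
- Treated: entry uniform over 0.5 to 5.9 months of age. Expected 14-month survival = S(14) × mean of exp(λ × entry age) = 0.2400 × 1.403 = 33.68%.
- Controls from birth: 24.00%. Difference +9.68 points.
- Controls entering at 3 to 9 months: 0.2400 × 1.872 = 44.94%. Difference −11.26 points.

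Fisher rates come from exact binomial enumeration, 25 against 23. Log-rank rates come from simulation on the age scale (6000 runs, 4000 for the Weibull cases; standard error about 0.6 points at 25%). The table shows false-finding rates in the direction of the bias.

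| Assumption | Controls enter | Direction | Fisher | Log-rank, no delayed entry |
|---|---|---|---|---|
| Constant hazard | birth | favourable | 8.1% | 25.2% |
| Constant hazard | 3–9 months | unfavourable | 8.8% | 20.1% |
| Constant, set so control survival is 6/23 | birth | favourable | 8.4% | 23.6% |
| Constant, set so control survival is 6/23 | 3–9 months | unfavourable | 11.1% | 35.9% |
| Weibull shape 1.5 | birth | favourable | 3.7% | 10.7% |
| Weibull shape 1.5 | 3–9 months | unfavourable | 6.1% | 17.0% |
| Weibull shape 2 | birth | favourable | 2.5% | 5.1% |
| Weibull shape 2 | 3–9 months | unfavourable | 4.6% | 11.3% |

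The recalibrated rows are there because constant hazard with late entry implies 44.94% control survival, well above the SAP's 26.1%. With controls entering over the same ages as treated infants, both tests are at 1.6% to 2.9% per side under constant hazard. With delayed entry the log-rank is at about 3% per side in every case (2.2% to 3.5% across runs).

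**3. How robust the Fisher test is.** Suppose k of the 16 control events preceded a comparable entry age and were removed, with the control who left kept as a failure. The control result becomes 6/(23 − k).

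| k | Control rate | p for 20/25 treated | Fewest treated survivors for p ≤ 0.05 |
|---|---|---|---|
| 0 | 6/23 = 26.1% | 0.0004 | 14 |
| 5 | 6/18 = 33.3% | 0.0039 | 17 |
| 9 | 6/14 = 42.9% | 0.033 | 20 |
| 10 | 6/13 = 46.2% | 0.064 | 21 |

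A result of 24/25 holds to k = 14 (p = 0.048).

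**The case against.** A reader might infer that the design carries a guaranteed-survival bias in favour of AVXS-101. The documents do not support that. Control entry ages are not given, and enrolling previously identified patients can equally mean that controls had to survive to a late entry. The only clue is the control who left at 4 months of age, which shows that at least one was under observation by then.

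Four other points carry weight.

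- The log-rank analysis may never run. It is there to relax the rule that leavers count as failures, and it carries no confirmatory weight.
- The age scale is a likely reading of the censoring rule, but the SAP states no time origin. The log-rank rates above apply only if that reading is right.
- The protocol does state an intention to match on age, which could bear on entry. But no rule appears, SAP 2 says the SAP supersedes the protocol's statistics, SAP 5.6 takes all eligible patients, and SAP 13 does not record the change. The intention alone does not show alignment.
- The largest rates need a constant hazard, under which 45% of untreated infants fail by 5.9 months. The documents neither support nor exclude that shape. At Weibull shape 2 the figure is 23%, and the Fisher favourable rate falls to 2.5%.

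All four limit the size of the point. None supplies the missing entry ages or time origin.

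**Conclusion.** The plan does not show that entry is aligned, and its one time-to-event check, as written, would not reveal or correct a misalignment. That much rests on the text alone. The size depends on assumed entry ages and hazard shape: if run on the age scale, the log-rank could be wrong in either direction in about 5% to 36% of null trials, against about 3% per side with delayed entry. The formal Fisher test is much less exposed, at 2.5% to 11.1% over the same cases.

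It would go too far to infer that the planned survival conclusion is unsafe. At the planned 80%, 10 of the 16 control events would have to be removed to lose significance. Protocol 5.4 reports all 15 Phase 1 patients alive and free of permanent ventilation 24 months after dosing, so a higher treated count is plausible. The sitting endpoint is not touched. The point is worth fixing because the remedy is cheap and gives a better supporting analysis.

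**What to change.** 1. **SAP 8.2.1.** Run the time-to-event analysis unconditionally. State age as the time scale. Use delayed entry at infusion age for treated infants and at PNCR enrolment (first-observation) age for controls. Report it beside the unchanged Fisher test, with numbers at risk by month of age. List any control whose event precedes enrolment, since such a patient contributes no risk time. Note that small early risk sets can make the delayed-entry Kaplan-Meier curve unstable.
2. **SAP 5.6.** Tabulate each control's entry age, event or censoring age and, where recorded, ventilation status at entry.
3. **Matching.** Reconcile the wording across the protocol synopsis, protocol 14.2 and 14.3.2, and SAP 3.7, 5.6 and 8.2.1. Either define the matching or delete it, and record the outcome in SAP 13.

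The Fisher test, alpha, hierarchy and leaver rule stay as they are.

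**Cost.** SAP wording and one re-derivation from PNCR data. It depends on first-observation dates being available, which SAP 6.2.1 suggests but does not prove. Fewer controls are at risk early: under constant hazard, 16.9, 9.4 or 0 expected at 3 months of age for entry at birth, 0.5–5.9 or 3–9 months. The contrast may also be less favourable. At 80% treated event-free survival, power of the delayed-entry log-rank is 91%, 93% or 88% in those three cases, against 99%, 93% or 70% without it.
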